6.11. Appendix 11 Covid-19

This appendix describes the analyses and presentation of immunogenicity and clinical endpoints for objectives related to the assessment of immune response to Covid-19 vaccination in subjects in the AC-058B303 study.

Specific objectives are:

- To describe binding antibody concentrations to SARS-CoV-2 S protein as measured by ELISA
- To describe binding antibody concentrations to SARS-CoV-2 N protein as measured by ELISA
- To describe Covid-19 infection Adverse events (AEs).

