The results generated for the Human SARS-CoV-2 PreSpike IgG ELISA are reported with concentration units in "ELU/mL". When required, a correlation factor of 1/7.9815 [2] will be applied to convert the reported results from ELU/mL to BAU/mL. For example, a sample with reported anti-PreSpike IgG antibody concentration of 7981.5 ELU/mL will have a concentration equivalent to 1000 BAU/mL.

The following formula may be used for converting concentration units from ELU/mL to BAU/mL:

Result (BAU/mL) = Result (ELU/mL) / 7.9815

Human SARS-CoV-2 Nucleocapsid IgG ELISA

The results generated for the Human SARS-CoV-2 Nucleocapsid IgG ELISA are reported with concentration units in "ELU/mL". When required, a correlation factor of 1/10.3383 [3] will be applied to convert the reported results from ELU/mL to BAU/mL. For example, a sample with reported anti-Nucleocapsid IgG antibody concentration of 10338.3 ELU/mL will have a concentration equivalent to 1000 BAU/mL.

The following formula may be used for converting concentration units from ELU/mL to BAU/mL:

Result (BAU/mL) = Result (ELU/mL) / 10.3383

Antibodies assessment related to vaccine sequence:

Pre-vaccine antibodies assessment: for each subject, the antibodies assessment which is prior to and closest start date of 1st vaccine regimen, is considered as Pre-vaccine antibodies assessment. Antibodies assessment post 1st vaccine regimen: for each subject, the antibody assessments on or after start of first vaccine regimen and before 1st booster are considered as antibody assessments post-1st vaccine regimen. The average of all values in a time frame of 365 days after the start of first vaccine regimen will be used as "Antibodies assessment post-1st vaccine regimen" in the analysis.

Antibodies assessment post 1st booster: for each subject, the antibody assessments on or after start of 1st booster and before the 2nd booster are considered as antibody assessments post-1st booster. The average of all values in a time frame of 365 days after the start of first booster will be used as the "Antibodies assessment post 1st booster" in the analysis.

Antibodies assessment post 2nd booster: for each subject, the antibody assessments on or after start of 2nd booster and before the 3rd booster are considered as antibody assessments post-2nd booster. The average of all values in a time frame of 365 days after start of second booster will be used as the "Antibodies assessment post 2nd booster" in the analysis.

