Antibodies assessment post 3rd booster: for each subject, the antibody assessments on or after start of 3rd booster and before the 4th booster are considered as antibody assessments post-3rd booster. The average of all values in a time frame of 365 days after start of third booster will be used "Antibodies assessment post 3rd booster".

Prior Covid-19 infection evidence related to vaccine sequence:

If a subject encountered one or more Covid-19 infection AEs and the start date of AE is prior to or on the start date of 1st vaccine regimen, the subject is considered to have Prior Covid-19 infection evidence related to 1st vaccine regimen.

If a subject encountered one or more Covid-19 infection AEs and the start date of AE is prior to or on the date of 1st booster, the subject is considered to have Prior Covid-19 infection evidence related to 1st booster, irrespective if the start date of AE is prior to 1st vaccine regimen.

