6.11.2.2. Analysis of Immunogenicity Related to Covid-19 Vaccination

A demographic table of study subjects who received Covid-19 vaccination will be provided including:

- number and percentage of subjects having pre-vaccination antibody assessment
- number and percentage of subjects having post-1st vaccine regimen assessment
- number and percentage of subjects having post-1st booster assessment
- number and percentage of subjects having post-2nd booster assessment
- number and percentage of subjects having post-3rd booster assessment
- age at time of 1st vaccination
- sex
- exposure (years) to ponesimod at time of 1st vaccination
- number and percentage of subjects in different vaccine type of the 1st vaccine regimen
- number and percentage of subjects with or without evidence of Covid-19 infection prior to 1st vaccine regimen
- number and percentage of subjects in different categories of lymphocyte count In the above frequency tabulations, percentage is calculated based on number of subjects in Covid-19 Vaccine Analysis Set.

For S-ELISA and N-ELISA assays, the following results will be presented:

- N, geometric mean and corresponding 95% CI of the actual values of pre-vaccination, post-first vaccine regimen, post-first, post-second and post-third booster. Note that the analysis by timepoint will be performed only if more than 5 subjects have antibody concentration measured at that timepoint.
- Dot plots with dots for subject values with the corresponding geometric mean, 95% CI, minimum and maximum for each assay, for pre-, post- 1st vaccine regimen, post- 1st booster and post- 2nd booster will be presented. In the graphs, values in BAU/ml unit will be displayed on the log10 scale. Note that the analysis by timepoint will be performed only if more than 5 subjects have antibody concentration measured at that timepoint.
- The above analyses will be repeated for S-ELISA antibody concentrations for the following subgroups: vaccine type of the 1st vaccine regimen, evidence of Covid-19 infection prior to 1st vaccine regimen and categories of lymphocyte count. Box plot will be generated to visualize S-ELISA antibody concentrations for the above-mentioned subgroups. Note that the analysis by timepoint will be performed only if more than 5 subjects have antibody concentration measured at the timepoint.

Analyses of S-ELISA and N-ELISA antibody concentration will be presented in BAU/ml unit only.

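### Post-dose antibody averages have no rule for samples taken after a later Covid-19 infection, so the S-ELISA means mix vaccine response with infection response

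*SAP*

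**What the plan says.** SAP section 6.11 introduces the appendix as serving "objectives related to the assessment of immune response to Covid-19 vaccination in subjects in the AC-058B303 study". The definitions are in section 6.11.2.1.

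- **Which samples count.** For the primary regimen, "the antibody assessments on or after start of first vaccine regimen and before 1st booster are considered as antibody assessments post-1st vaccine regimen".
- **How they are reduced.** "The average of all values in a time frame of 365 days after the start of first vaccine regimen will be used" as the subject's value. For the first booster: "The average of all values in a time frame of 365 days after the start of first booster will be used". The second booster follows the same pattern, and for the third: "The average of all values in a time frame of 365 days after start of third booster will be used". Each window closes at the next dose, so 365 days is a maximum.
- **Infection flags.** Two are defined, both from AE onset dates. The first reads "If a subject encountered one or more Covid-19 infection AEs and the start date of AE is" before or on "the start date of 1st vaccine regimen, the subject is considered to have" prior infection evidence for that regimen. The second applies the same test to the first-booster date, whether or not the infection preceded the primary regimen. No flag is defined for the second or third booster.
- **Use of infection status.** In section 6.11.2.2 the S-ELISA analyses are repeated by type of first vaccine and by "evidence of Covid-19 infection prior to 1st vaccine regimen and categories of lymphocyte count". No other infection split is listed.
- **Infections after vaccination.** Section 6.11.3 tabulates Covid-19 infection AEs before and after the first dose. It does not link them to the antibody samples.

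**The concern.** The stated interest is the response to vaccination, and the measurement window can last a year. An infection inside that window can raise S-antibody for reasons unrelated to the vaccine dose to which the sample is assigned. The SAP already treats infection as relevant to S-antibody, since it stratifies S-ELISA by infection before the regimen. It has no counterpart for infection during the window, so a post-infection sample enters the average like any other.

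What is at stake is how the post-regimen and post-booster S-ELISA geometric means can be read, overall and in the stratum without infection before the first regimen. A reader cannot tell how much of a given mean reflects vaccine and how much reflects later infection.

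**Working it through.** The SAP states no expected antibody level, infection share or sample size for this analysis, so there is no planned figure to reproduce. The check has two parts.

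**1. Does any rule remove or separate post-infection samples?**

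| Infection starts | First-regimen flag | First-booster flag | Split used in 6.11.2.2 | Later samples in that dose's average? |
|---|---|---|---|---|
| Before or on first regimen | Yes | Yes | With prior infection | Yes |
| After first regimen, before or on first booster (boosted subject) | No | Yes | Without prior infection | Yes |
| After first regimen, never boosted | No | Not applicable | Without prior infection | Yes |
| After first booster | No | No | Without prior infection | Yes |

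The first-booster flag does pick up the second row. It combines those infections with the ones in the first row, and no analysis listed in 6.11.2.2 uses it. N-ELISA, which section 6.11.1 ties to seroconversion, is summarised but is not used to classify or exclude samples. The gap is real in the text.

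**2. How large could this one source be?**

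Inputs, all assumed because the SAP gives none:
- f = share of subjects with one sample after an in-window infection;
- F = fold rise in S-antibody after infection;
- k = number of samples in the subject's window, otherwise at equal level.

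Section 6.11.2.1 asks for an average of values; the log10 transformation in 6.11.2.2 belongs to the geometric mean across subjects. Taking the within-subject average as arithmetic, an affected subject's value is multiplied by (k − 1 + F)/k. The geometric mean is then multiplied by

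inflation = ((k − 1 + F)/k)^f.

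With one of two samples affected (k = 2):
- f = 0.10, F = 3: ((1 + 3)/2)^0.10 = 2^0.10 = 1.07
- f = 0.20, F = 5: ((1 + 5)/2)^0.20 = 3^0.20 = 1.25
- f = 0.30, F = 10: ((1 + 10)/2)^0.30 = 5.5^0.30 = 1.67

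If the subject's only sample is post-infection (k = 1), the formula becomes F^f and the same inputs give 3^0.10 = 1.12, 5^0.20 = 1.38 and 10^0.30 = 2.00. That is the upper case, with no averaging to dilute the effect.

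Over f = 5% to 40%, F = 2 to 10 and k = 1 to 3, the factor runs from ((2 + 2)/3)^0.05 = 1.01 to 10^0.40 = 2.51. Without post-infection samples it is 1.00 by construction.

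**An opposing source in the same window.** The window opens on the day of the first dose, so a day-of-dose sample counts. If 10% of subjects have one of two samples near zero, their average is halved and the geometric mean is multiplied by 0.5^0.10 = 0.93. Between-dose and late samples can also lower the average.

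**The case against.** The strongest defence is that the specific objectives in section 6.11 are to describe binding antibody concentrations and infection AEs, and section 2 declares all analyses exploratory. Describing observed levels regardless of later infection is a legitimate choice. Affected samples can also be traced: N-ELISA is summarised at the same time points, the antibody listing gives assessment dates, and the AE listing gives onset dates. This stands as a reason to keep the all-sample average. It does not make that average readable as response to vaccination, which is how the appendix frames its purpose, and listings do not separate the means.

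The other summary has its own weakness. Stopping at infection conditions on an event after vaccination. If weaker responders are infected more often, the restricted mean could be distorted too. This also stands, and it argues for showing both.

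A reader might go further than the text allows in three ways:
- **That the reported vaccine response is biased upward overall.** Only this source has an upward sign, and only if infection raises S-antibody. Day-of-dose, between-dose and late samples can work the other way.
- **That no flag could catch an in-window infection.** The first-booster flag covers infections between regimen and booster in boosted subjects; it is simply not used.
- **That the SAP presents a subgroup as infection-free.** It labels the stratum only by infection before the first regimen, which is literally accurate.

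**Conclusion.** The point holds as a gap in the analysis rule. Every sample from a dose to the next dose, up to 365 days, enters the average, and no rule separates those taken after a later infection. The only infection split analysed concerns infection before the first regimen. The post-dose S-ELISA geometric means therefore mix two sources of antibody.

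If infection raises S-antibody and at least one sample follows it, this source pushes the mean above the same average without post-infection samples. The factors of 1.07, 1.25 and 1.67 are illustrations that rest on the assumed infection share, fold rise and one affected sample out of two. Neither the actual size nor the net direction of error can be fixed from the SAP. The analysis is a descriptive appendix, and none of the efficacy or safety endpoints in section 1.1 is touched. The change is worth making because it is cheap and makes the means interpretable.

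**What to change.** In section 6.11.2.1, keep the all-sample average and add, for each post-dose time point, a second S-ELISA summary whose window ends at the earliest of:
- the next vaccine dose;
- day 365;
- the day before onset of the first Covid-19 infection AE after that dose.

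Summarise the later samples separately, labelled as vaccination plus infection. As a sensitivity check, also end the window at N-ELISA seroconversion, with the threshold fixed in advance. Show the all-sample and restricted summaries together.

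**Cost.** A sentence or two in the SAP, a date comparison in programming, and an extra summary per time point. The AE dates and N-ELISA results are already collected. The downsides are fewer samples per time point, and some time points may drop to 5 or fewer subjects, which section 6.11.2.2 would then not analyse. AE dates also miss unreported infections, which is why the N-ELISA check is useful. The restricted summary describes subjects while they remain free of a reported post-dose infection and should be labelled that way.

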6.11.1. Immunogenicity Variables

For Covid-19 vaccination, the following humoral immune responses are measured, including titers of neutralizing antibodies and S- and N-ELISA titers.

Humoral Assay	Purpose
SARS-CoV-2 binding antibodies to S protein	Analysis of antibodies binding to SARS-
(ELISA)	CoV-2 S protein
SARS-CoV-2 seroconversion based on	Analysis of antibodies binding to SARS-
antibodies to N protein (ELISA)	CoV-2 N protein

6.11.2. Analysis of Immunogenicity Related to Covid-19 Vaccination:

6.11.2.1. Analysis related definitions:

Covid-19 vaccine analysis set: Study subjects who have a complete Covid-19 first vaccine regimen and at least one non-zero vaccine-specific antibody titers assessed within a timeframe (defined as any timepoint prior to the start of Covid-19 vaccine or within the 365 days after the 1st dosing or within 365 days after any boosters).

First Vaccine Regimen: For each subject, the 1st and 2nd doses of vaccine in the SDTM CM dataset are considered. Definition of 1st Vaccine Regimen for Janssen vaccine: Only the 1st dose is considered.

First Booster: The 1st subsequent dose of vaccine after first vaccine regimen is considered as the First Booster.

Second Booster: The 2nd subsequent dose of vaccine after first vaccine regimen is considered as the Second Booster.

Lymphocyte counts for a subject corresponding to a specific vaccination will be determined as the minimum of the last two available values within six months prior to the first vaccination date of first vaccine regimen. If only one value is available within this range, this value will be used. If none are available in the range, the lymphocyte value corresponding to the particular vaccination will be considered missing. Categories of "Lymphocyte Count < 500 mm³" and "Lymphocyte Count >= 500 mm³" will be used in the analysis.

Analysis based on BAU/ml: In order to calibrate across different assays, the WHO has proposed International Standards (WHO IS). The WHO IS assigned unit for quantifying immunoglobulins

is BAU/ml. Per Nexelis, the conversion of ELISA units (EU/ml) to BAU/ml is as shown below (see Attachment below):

Human SARS-CoV-2 Pre-Spike IgG ELISA

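### Evidence of Covid-19 infection before vaccination is taken from adverse event reports alone, although the same appendix measures N-protein antibodies at a pre-vaccine assessment

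*SAP*

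**What the plan says.** **Infection status.** SAP Section 6.11.2.1 gives one rule. It begins "If a subject encountered one or more Covid-19 infection AEs and the start date of AE is" and is met when that date is on or before the start of the first vaccine regimen. A parallel rule is given for the first booster. Section 5.4.2.1 limits an AE to what the investigator enters on the AE form.

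**N-protein assay.** The assay table in Section 6.11.1 lists a second ELISA whose label begins "SARS-CoV-2 seroconversion based on" and continues with antibodies to N protein. The matching objective in Section 6.11 is descriptive: "To describe binding antibody concentrations to SARS-CoV-2 N protein as measured by ELISA".

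**Pre-vaccine sample.** Section 6.11.2.1 defines it for each subject: "the antibodies assessment which is prior to and closest start date of 1st vaccine regimen, is considered as Pre-vaccine antibodies assessment". No limit is set on how old it may be. Section 6.11.2.2 tabulates the "number and percentage of subjects having pre-vaccination antibody assessment", so the plan does not assume that every subject has one.

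**Outputs.** Section 6.11.2.2 reports, for both the S and the N assay, "N, geometric mean and corresponding 95% CI of the actual values of pre-vaccination, post-first vaccine regimen, post-first, post-second and post-third booster". The infection flag then enters a subgroup display: "The above analyses will be repeated for S-ELISA antibody concentrations for the following subgroups: vaccine type of the 1st vaccine regimen, evidence of Covid-19 infection" before the first regimen, and lymphocyte category. It also gives the counts of subjects with and without evidence of infection in the demographic table.

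**The concern.** An infection that was silent, untested or simply not reported leaves no AE. The rule places such a subject with those who have no evidence of infection, even when the subject's own pre-vaccine N result points the other way. The plan collects, summarises and lists that result, and its assay table describes the assay in terms of seroconversion. Yet Section 6.11 contains no positivity cut-off for N and no step that links N to infection status.

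What is at stake is how the S-ELISA summaries split by prior infection are read. If earlier infection raises S antibody, hidden infections lift the geometric mean of the group without evidence and bring the two groups' displayed values closer together. The with/without counts are wrong by the same subjects.

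**Working it through.** The plan states no figure for this point, so there is none to reproduce. The check is textual, followed by an illustration.

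**Textual check of Section 6.11**

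1. Source of the flag: Covid-19 AEs only (6.11.2.1).
2. Other infection evidence collected: N-ELISA (6.11.1), with a defined pre-vaccine assessment (6.11.2.1).
3. Uses of N: geometric means with confidence intervals, dot plots and a listing (6.11.2.2). None assigns infection status.
4. Uses of the flag: the S-ELISA subgroup tables and plots, and the with/without counts (6.11.2.2).

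A subject with a high pre-vaccine N value and no Covid-19 AE is therefore listed with that value and counted as without evidence. The pre-vaccine sample precedes every recorded vaccine dose, so those doses cannot explain a raised N result in it.

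**Illustration of size (inputs are assumptions; none is in the document)**

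- p = true share infected before vaccination, 10-30%.
- s = share of those infections captured as AEs, 40-80%.
- R = true ratio of S geometric means, infected to uninfected, 3 to 10, taken as the same for reported and unreported infections.

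The share of the group without evidence that was in fact infected is q = p(1 − s) / (1 − ps).

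- p = 0.1, s = 0.8: 0.02 / 0.92 = 2.2%.
- p = 0.3, s = 0.4: 0.18 / 0.88 = 20.5%.

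Section 6.11.2.2 computes geometric means from log10 values, so the group's geometric mean is multiplied by R^q.

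| q | R = 3 | R = 5 | R = 10 |
|---|---|---|---|
| 2.2% | 1.02 | 1.04 | 1.05 |
| 20.5% | 1.25 | 1.39 | 1.60 |

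With s = 1, q is 0 and there is no bias. For any R above 1 and s below 1 the direction is upward; only the size depends on the inputs.

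**The case against.** The strongest case on the other side is that nothing here is an error. The rule is clear and consistently applied, and the plan gives N only a descriptive role, so no promised step is missing. What of this stands:

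- **The label is modest.** The plan speaks of subjects with or without evidence of infection. A reader might infer that it presents the second group as never infected; it does not. The label still overlooks evidence that the plan itself collects.
- **The output is descriptive.** Section 2 states that no hypotheses are pre-specified and that all analyses are exploratory. No test or ratio between the infection subgroups is planned. A reader might infer that the vaccine response on ponesimod is made to look better than it is. The document does not support that: the overall S-ELISA results do not use the flag, and no conclusion about infection-naive subjects is planned.
- **The information is partly visible.** Pre-vaccine N is summarised and individual values are listed, so a reader could match them to Covid-19 AEs by hand. What is missing is a derived status.
- **Serology has limits.** The pre-vaccine sample may be old, and an old negative cannot exclude a later infection. Samples may be few: timepoints are analysed only if more than 5 subjects have a measurement. Post-regimen S values are averaged over up to 365 days with no exclusion for infection after vaccination, so neither definition yields a strictly infection-naive group.

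These points limit the consequence and shape the remedy. They do not justify setting aside a pre-vaccine N result that is already in hand.

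**Conclusion.** The point holds as a minor weakness in one descriptive appendix analysis. Infection status before the first vaccine regimen rests on AE reports alone, and serological evidence already measured is not used. The S-ELISA geometric mean in the group without evidence is biased upward if prior infection raises S antibody and some infections went unreported.

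The document gives neither the prevalence of infection, nor the share reported as AEs, nor the antibody ratio. The 2-21% misclassification therefore only illustrates the stated assumptions and is not an estimate for this trial. How many subjects have a usable pre-vaccine sample, and so could be reclassified, is also unknown. The overall S-ELISA, efficacy and main safety results are unaffected.

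**What to change.** In Section 6.11.2.1, define evidence of infection before the first vaccine regimen as either of:

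- a Covid-19 AE starting on or before the first vaccine date; or
- a pre-vaccine N-ELISA result above the testing laboratory's positivity cut-off, with the cut-off stated in the SAP.

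Then:

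- Classify by AE alone any subject with no pre-vaccine sample, or with only a negative sample older than a pre-specified lookback, and flag that subject as 'serology unknown'.
- Keep the AE-only definition as a sensitivity display.
- Cross-tabulate AE status against pre-vaccine N status, so that the extent of disagreement can be seen.

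The cost is SAP wording, one cut-off obtained from the laboratory, a chosen lookback, one derived flag and one small table. No new data are collected. The limitation is that only subjects with a pre-vaccine sample can be reclassified.
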